# 4.3 Patient Withdrawal and Replacement

Patients may withdraw from the entire study, including follow up, at any time without penalty and for any reason without prejudice to his or her future medical care.

In all cases, the reason(s) for withdrawal, including the primary reason, must be recorded on the electronic Case Report Form (eCRF). If a patient is prematurely withdrawn from the study for any reason, the Investigator must make every effort to perform the evaluations described for the appropriate discontinuation visit.

If a patient withdraws consent and still agrees to undergo a final examination, this will be documented in the eCRF.

A patient may also be withdrawn from study by the Investigator, Sponsor, Regulatory Authorities, or Institutional Review Boards (IRBs).

Patients will also be withdrawn if the entire study is terminated prematurely as described in Section 9.10.

Withdrawn patients will not be replaced.

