#### 4.3.1 Patient Withdrawal Criteria

The Investigator will withdraw a patient from the clinical study if any of the following situations occur:

- 1. When the patient withdraws his or her consent
- 2. When the occurrence of an AE, such as noted below, leads the Investigator to judge it necessary for the patient to have surgical intervention or to withdraw the patient from the clinical study:
  - Significant neurologic deficit, e.g., progressive weakness or sudden loss of muscle strength in L1–L2, L2–L3, L3–L4, L4–L5 or L5–S1 innervated muscles, bowel or bladder dysfunction, or other signs and symptoms of cauda equine/conus medullaris involvement, or
  - Abnormal X-ray or MRI findings coupled with correlating clinical symptoms posing safety concerns
- 3. When a poor response to the investigational drug leads the Investigator to judge it necessary to perform a surgical intervention for back pain/leg pain or to withdraw the patient from the clinical study

- 4. If the Investigator judges it inappropriate to include a patient in the efficacy/safety assessment
- 5. If a patient becomes pregnant
- 6. Others:
  - No investigational drug could be administered.
  - The continuation of the study makes the risk to a patient's health unacceptable.
  - The Sponsor prematurely terminates the study.
  - The Investigator judges it necessary to withdraw a patient from the study.

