# 6.1.1.4 Recording Adverse Events

The AE recording into the eCRF will extend from the signing of the ICF until completion of final visit. All AEs will be followed until they are resolved or stabilized; however, if AEs are ongoing at the time of the last study visit, only treatment-related AEs will be followed beyond 26 weeks after investigational drug administration.

All AEs, regardless of the relationship to study drug, will be recorded in the eCRF system.

All AE reports should contain a brief description of the event, date and time of onset, date and time of resolution, intensity, treatment required, relationship to study drug, action taken with the study drug, outcome, and whether the event is classified as serious.

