#### 7.2.7 Discontinuation Visit

- Complete pain assessment (VAS) and ODI
- Record concomitant drug and therapy information, including drugs or therapy used to treat an AE
- Record AEs and SAEs since previous visit
- Document occurrence of lumbar surgery
- Perform vital sign assessments (temperature, blood pressure, heart and respiration rate)
- Perform neurological examination
- Perform imaging tests (X-ray and MRI)
- Obtain laboratory specimens (blood for hematology, hepatic, and chemistry panels)
- Obtain blood specimen for serum anti-SI-6603 antibody

Patients who discontinue early from the study should, if possible, have a Discontinuation Visit. This visit should take place as soon as possible after it was learned that the patient will not be able to complete the study (see also Section 4.3).

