# 9.10 Premature Termination of the Study

If the Investigator, the Sponsor, or the Medical Monitor becomes aware of conditions or events that suggest a possible hazard to patients if the study continues, the study may be terminated after appropriate consultation between the relevant parties. The study may also be terminated early at the Sponsor's discretion in the absence of such a finding.

Conditions that may warrant termination of the study include, but are not limited to:

- The discovery of an unexpected, significant, or unacceptable risk to the patients enrolled in the study (e.g., AE other than those listed in Table 1)
- The occurrence of an AE, as noted below:
  - a. Significant neurologic deficit; for example, progressive weakness or sudden loss of muscle strength, bowel or bladder dysfunction, or other signs and symptoms of cauda equine / conus medullaris involvement, or
  - b. Abnormal X-ray findings of instability, defined as vertebral body angle formed by flexion of  $\geq 5^{\circ}$  or vertebral body translation of  $\geq 3 \text{ mm}$
  - c. Abnormal X-ray or MRI findings which patients exhibit correlating clinical symptoms posing safety concerns, leading the Investigator to judge it necessary for the patient to have surgical intervention

At time of occurrence of these treatment-related AEs, the Sponsor will notify the DSMB and provide the necessary information. DSMB chairperson will determine to make one of two decisions - (1) Continue the study as planned or (2) Request an ad hoc meeting. The Sponsor will judge discontinuation of the study based on the recommendation of the DSMB. The details of the DSMB procedure will be provided in the DSMB charter.

- Failure to enroll patients at an acceptable rate
- A decision on the part of the Sponsor to suspend or discontinue development of the drug

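### If the whole study is terminated for a possible hazard, injected patients must be withdrawn, and one prompt visit replaces their remaining scheduled safety assessments

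*Combined protocol and SAP*

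**What the plan says.** **Withdrawal on termination.** Section 4.3 states: "Patients will also be withdrawn if the entire study is terminated prematurely as described in Section 9.10". Section 4.3.1 lists situations in which the Investigator will withdraw a patient, and item 6 includes "The Sponsor prematurely terminates the study". Neither section separates patients awaiting injection from those already injected.

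**Grounds for termination.** Section 9.10 covers "conditions or events that suggest a possible hazard to patients if the study continues, the study may be terminated", after consultation between the parties. The conditions it lists include, at item b, "Abnormal X-ray findings of instability, defined as vertebral body angle formed by flexion of" 5° or more, or vertebral body translation of 3 mm or more. For the listed AEs the data safety monitoring board (DSMB) chairperson's options are given as "1) Continue the study as planned or (2) Request an ad hoc meeting". The Sponsor then decides on the DSMB's recommendation, and further procedure is left to a DSMB charter.

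**What a withdrawn patient receives.** Section 4.3 says that "the Investigator must make every effort to perform the evaluations described for the appropriate discontinuation visit". Section 7.2.7 makes this a full visit: VAS, ODI, AEs, vital signs, neurological examination, X-ray, MRI, laboratory tests and antibody. On timing it says: "This visit should take place as soon as possible after it was learned that the patient will not be able to complete the study". Table 3 allows +14 days. Section 9.9 lets the study close on this visit in place of Week 26.

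**AE recording.** Section 6.1.1.4: "The AE recording into the eCRF will extend from the signing of the ICF until completion of final visit".

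**The concern.** The drug is given once, on Day 0 (section 5.6). A hazard stop protects people not yet injected. For those already injected there is no later dose to withhold, so withdrawal removes only observation.

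The patients injected most recently would then get the least imaging and neurological follow-up for the hazard that caused the stop. Section 3.3 treats 26 weeks as the adequate safety period, and section 2.1 makes 26-week safety the primary objective.

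Some of the protocol's background evidence concerns the interval that would be lost:

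- Section 1.1.1.3 reports enzyme activity at the injection site for up to 30 days in dogs, with a similar result in monkeys.
- Section 1.1.1.4 reports endplate and vertebral body effects in monkeys from Week 1 to Week 13. This is animal histology, at doses up to just below 500 times the clinical dose, not severe, and recovering by Week 26.
- Section 1.3.1.4 reports that past instability came without leg or back pain, so reporting driven by symptoms could miss it.

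**Working it through.** **1. What stops and what continues for an injected patient withdrawn before Week 26**

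| Item | After the Discontinuation Visit | Source |
|---|---|---|
| X-ray, MRI (Weeks 6, 13, 26) | stops | Table 3 |
| Neurological examination, VAS, ODI (Weeks 1, 6, 13, 26) | stops | Table 3 |
| Antibody (Weeks 13, 26) | stops | Table 3 |
| Laboratory tests (Weeks 1, 6, 13) | lost only if Week 13 is not yet reached | Table 3 |
| New non-serious AEs | recording stops | 6.1.1.4 |
| Serious AEs to 26 weeks after the dose | continues | 6.1.1.5 |
| Lumbar surgery to Week 26 | continues | Table 3, footnote e |
| Ongoing treatment-related AEs | continues | 6.1.1.4, 6.1.1.6 |

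The items that continue would not detect later instability without symptoms.

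**2. The most recently injected patient.** For an injection the day before the stop, the last imaging could fall by Day 1 + 14 = Day 15. The Week 6 window opens at Day 42 − 14 = Day 28. Table 3 footnote c adds up to 14 days, but only if imaging must be repeated.

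**3. Share losing imaging rounds.** Assume even accrual, no dropouts, and a stop while accrual is running and after it has lasted at least one full follow-up period. The share in each interval is then its length divided by the follow-up length, whatever the accrual period. Rounds lost = rounds still due − 1, because the Discontinuation Visit supplies one. The columns take all visits as early, nominal or late within ±14 days.

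| | Weeks 4, 11, 24 | Weeks 6, 13, 26 | Weeks 8, 15, 28 |
|---|---|---|---|
| Lose two (3 − 1) | 4/26 = 15% | 6/26 = 23% | 8/28 = 29% |
| Lose one (2 − 1) | 7/26 = 27% | 7/26 = 27% | 7/28 = 25% |
| Last round brought forward (1 − 1) | 13/26 = 50% | 13/26 = 50% | 13/28 = 46% |
| None left to lose | 2/26 = 8% | 0 | 0 |
| **Lose at least one** | **11/26 = 42%** | **13/26 = 50%** | **15/28 = 54%** |

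In the early column, 2/26 have had every round but are short of Week 26. Counting them as finished gives 11/24 = 46%, inside the range. Mixed timing could go outside it: Week 13 early with Week 26 late gives 11/28 = 39%, and the reverse gives 15/24 = 63%.

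**4. Counts, as illustration only.** The accrual period is not stated, so 52, 78, 104 and 156 weeks are assumed for 1000 patients. The weekly rate is 1000/weeks = 19.23, 12.82, 9.62, 6.41.

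- Injected and short of Week 26 (rate × 26): 500, 333, 250, 167.
- Losing at least one round, early visits (rate × 11): 212, 141, 106, 71.
- Nominal visits (rate × 13): 250, 167, 125, 83.
- Late visits (rate × 15): 288, 192, 144, 96, out of rate × 28 = 538, 359, 269, 179.

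**5. Radiation cost of continuing.** The per-visit figure in section 1.3.1.5 reproduces as three lateral views plus one anteroposterior: 3 × 0.290 + 0.690 = 1.56 mSv. Three remaining rounds give 3 × 1.56 = 4.68 mSv, all already planned. Less the Discontinuation Visit round, 4.68 − 1.56 = 3.12 mSv.

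**The case against.** The strongest reply is that the rule applies only after two discretionary steps: a serious signal, and a decision to end the entire study instead of pausing injections. Section 9.10 says the study may be terminated. A reader might infer that a hazard forces termination, and so withdrawal; the documents do not say that.

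A reader might also infer that the DSMB has no route that keeps visits running. The two options in section 9.10 are the chairperson's first response to the listed AEs. The section does not limit what an ad hoc meeting may recommend, and the charter is not available here. Section 9.8 provides for amendments, and section 9.12 contemplates them when a significant safety issue arises. This stands, and it lowers the priority. However, an amendment must be written and approved, where appropriate by the ethics bodies and authorities, before it is implemented, while section 7.2.7 calls patients to a prompt final visit.

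A third tempting inference is that termination ends all safety follow-up. It does not, as step 1 of the working shows. In addition, an imaging finding beyond threshold at the Discontinuation Visit is an AE (section 6.1.1.2) and, if ongoing and judged related, is followed further.

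The clinical weight of the gap is uncertain. Sections 1.1.2.5 and 1.3.1.4 report no accompanying pain, while section 1.1.2.7 reports a trend to more treatment-related low back pain at 1.25 U among patients with disc-height or angle AEs. Finally, reduced 26-week precision after a stop would come partly from halted enrolment, not from this clause alone.

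**Conclusion.** The point holds as a conditional one. If the Sponsor terminates the whole study for a possible hazard, the protocol as written withdraws injected patients and ends their scheduled safety assessments after one prompt visit, with no further dose to withhold. The loss is mainly later-onset findings that are non-serious or asymptomatic, of which radiographic instability is the clearest example and is itself a condition for termination.

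The probability is low, and nothing changes if the study completes. The absolute number affected is not derivable. The 42% to 54% share rests on even accrual, no dropouts and visits held consistently early to consistently late in their windows. For patients already past the Week 13 visit, the last round is mainly brought forward. Priority lies between an optional clarification and a recommended change; the low cost is the main argument for making it.

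**What to change.** In sections 4.3, 4.3.1 item 6 and 9.10, state that termination for a possible hazard stops enrolment and injections, and that patients already injected complete the existing Table 3 safety assessments and AE recording to Week 26. Make this subject to consent, and keep individual withdrawal for unacceptable risk. Let the DSMB or Sponsor drop assessments irrelevant to the hazard, for example X-rays after an acute allergic signal.

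The cost is a few sentences of amendment, plus running already planned visits and central reads after the stop. Per patient this is at most two imaging rounds and 3.12 mSv beyond the current wording, all within the dose already planned.

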#### 4.3.1 Patient Withdrawal Criteria

The Investigator will withdraw a patient from the clinical study if any of the following situations occur:

- 1. When the patient withdraws his or her consent
- 2. When the occurrence of an AE, such as noted below, leads the Investigator to judge it necessary for the patient to have surgical intervention or to withdraw the patient from the clinical study:
  - Significant neurologic deficit, e.g., progressive weakness or sudden loss of muscle strength in L1–L2, L2–L3, L3–L4, L4–L5 or L5–S1 innervated muscles, bowel or bladder dysfunction, or other signs and symptoms of cauda equine/conus medullaris involvement, or
  - Abnormal X-ray or MRI findings coupled with correlating clinical symptoms posing safety concerns
- 3. When a poor response to the investigational drug leads the Investigator to judge it necessary to perform a surgical intervention for back pain/leg pain or to withdraw the patient from the clinical study

- 4. If the Investigator judges it inappropriate to include a patient in the efficacy/safety assessment
- 5. If a patient becomes pregnant
- 6. Others:
  - No investigational drug could be administered.
  - The continuation of the study makes the risk to a patient's health unacceptable.
  - The Sponsor prematurely terminates the study.
  - The Investigator judges it necessary to withdraw a patient from the study.

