#### **3.3** Justification of the Study Design

This study is planned to investigate the safety and efficacy of SI-6603 as a single intradiscal injection for the treatment of lumbar disc herniation.

An open-label single treatment group design has been chosen to assess the safety of the treatment in a large number of patients.

The patients in the current study are people who have lumbar disc herniation and who have seen no improvement from adequate conservative treatment prior to screening. There will be no limitations on concomitant medications used to treat lumbar disc herniation, in order to enable data collection from a population that more realistically represents the target population.

The study has been designed to ensure the safety of the patients. The dosing scheme has been chosen on the basis of data currently available. Efficacy will be assessed as secondary endpoints using validated tools (VAS, ODI) and neurological examinations.

A 26-week follow-up period is considered adequate to assess safety effects of a single-dose treatment.

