# 5.4 Blinding and Breaking the Blind

The study is not blinded.

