#### 8.1.2 Analysis Sets

The following populations will be assessed:

- Safety: All patients who were treated with an investigational drug.
- Intent-to-Treat (ITT): All patients who were treated with an investigational drug.

If considered necessary, further populations may be defined in the SAP.

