#### Missing data conventions

In general, data will not be imputed for safety analyses.

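### Withdrawal criterion 4, like the last bullet of criterion 6, can end a treated patient's scheduled safety follow-up on an undefined investigator judgement, so follow-up may be truncated informatively

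*Combined protocol and SAP*

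**What the plan says.** Section 4.3.1 opens with "The Investigator will withdraw a patient from the clinical study if any of the following situations occur", so each listed item is mandatory once met. Item 4 reads "If the Investigator judges it inappropriate to include a patient in the efficacy/safety assessment". Items 1, 2, 3 and 5 deal with consent, AEs, poor response and pregnancy. Item 6 covers patients who could not be dosed, unacceptable risk and termination by the sponsor, and ends with a general clause: "The Investigator judges it necessary to withdraw a patient from the study".

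Section 8.1.2 defines the analysis set without reference to the investigator's opinion: "Safety: All patients who were treated with an investigational drug". The ITT set has the same definition. Section 4.3 adds "Withdrawn patients will not be replaced" and asks for a discontinuation visit whatever the reason for withdrawal. On missing data, section 8.2 states "In general, data will not be imputed for safety analyses". On design, section 3.3 states "An open-label single treatment group design has been chosen to assess the safety of the treatment in a large number of patients", and section 5.4 states "The study is not blinded".

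**The concern.** Study treatment is one injection on Day 0 (section 5.6). Withdrawing a patient after that day cannot reduce exposure; it reduces only what is observed. The situations that concern the patient's wishes or welfare have their own items. What is left for item 4 is a view on whose data are fit to be assessed, formed by someone who knows the treatment and the course so far.

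The patients most likely to attract that view are those with an untidy course, such as a deviation in the procedure or a confounding illness. If their risk of later findings differs from that of other patients, the end of follow-up is informative. The primary objective is to describe safety over 26 weeks, and there is no comparator arm in which selective loss would show. Data that were never collected cannot be recovered in the analysis.

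**Working it through.** **1. What continues after a treated patient is withdrawn**

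| Data | After withdrawal | Source |
|---|---|---|
| Lumbar surgery | Followed to Week 26 | Table 3, note e |
| SAEs | Reportable to 26 weeks after dosing, related or not | 6.1.1.5 |
| Treatment-related AEs already ongoing | Followed further | 6.1.1.4, 6.1.1.6 |
| X-ray and MRI (Weeks 6, 13, 26) | One set at the discontinuation visit, then none scheduled | Table 3, 7.2.7 |
| Antibody (Weeks 13, 26) | One sample at that visit | Table 3, 7.2.7 |
| VAS, ODI, neurological examination | Once at that visit | Table 3, 7.2.7 |
| New non-serious AEs | Recording runs to the final visit | 6.1.1.4 |

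For a withdrawn patient I read the final visit as the discontinuation visit, which fits section 9.9.

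The imaging row matters because section 6.1.1.2 makes a disc height loss of at least 30%, angulation, translation and Modic change AEs by definition. They are found by scheduled imaging. In past studies, treatment-related MRI abnormality was reported in 60/269 = 22.3% of patients and X-ray abnormality in 38/269 = 14.1% (section 1.3.1.4).

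**2. The plan's own precision figures (section 8.8)**

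The Clopper-Pearson limits for x events in n patients are:
- lower = Beta quantile(0.025; x, n − x + 1)
- upper = Beta quantile(0.975; x + 1, n − x)

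With n = 1000:
- x = 3: 0.3% (0.062% to 0.874%). The plan gives 0.06% to 0.87%, so it is reproduced.
- x = 15: 1.5% (0.842% to 2.462%). The plan gives 0.84% to 2.46%, so it is reproduced.

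**3. Illustration: events missed, patients kept in the denominator**

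The number missed is an assumption; the documents give none.

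| True events | Missed | Observed | 95% CI |
|---|---|---|---|
| 3 | 1 | 0.2% | 0.024% to 0.721% |
| 3 | 2 | 0.1% | 0.003% to 0.556% |
| 15 | 1 | 1.4% | 0.767% to 2.338% |
| 15 | 3 | 1.2% | 0.622% to 2.087% |
| 15 | 5 | 1.0% | 0.481% to 1.831% |

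For the first row the estimate falls by (0.3 − 0.2)/0.3 = one third. The upper limit falls by 0.874 − 0.721 = 0.153 percentage points.

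**4. How much use of the criterion that would take**

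Let a share w of treated patients be withdrawn, with r times the event risk of the others, and let all their events be missed. The share of events lost is s = wr/(wr + 1 − w).

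- w = 1%, r = 1: s = 0.01, so 0.3% becomes 0.297%.
- w = 1%, r = 3: s = 0.03/(0.03 + 0.99) = 2.9%, so 0.3% becomes 0.291%.
- w = 5%, r = 5: s = 0.25/(0.25 + 0.95) = 20.8%, so 0.3% becomes 0.2375% and 1.5% becomes 1.1875%.
- Losing one third on average needs wr = 0.5(1 − w). At w = 5% that is r = 0.475/0.05 = 9.5.

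Both w and r are assumptions. Treating every event as missed is a worst case, since SAEs, surgery and anything seen by the discontinuation visit are kept.

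**The case against.** A reader might infer that item 4 contradicts the all-treated safety population, or that withdrawn patients drop out of it. The documents do not support that. Item 4 ends participation in the study; 8.1.2 still counts every treated patient. Both can be followed.

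A reader might also infer that follow-up ends altogether. It does not. A discontinuation visit must be attempted, and it includes X-ray, MRI, antibody, VAS, ODI, neurological and laboratory assessments. SAEs and surgery are captured to 26 weeks. An event already seen is recorded as an AE, and withdrawal does not erase it. Reasons for discontinuation are summarised (section 8.1.1), so use of the criterion would be visible.

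It can further be said that deleting item 4 alone achieves nothing, because the last bullet of item 6 leaves the same discretion. The one-in-three loss is assumed, and its interval still contains 0.3%. The direction of bias is not general either: by-visit imaging and antibody percentages, if based on observed patients, could move either way. The detailed SAP is still to be finalised (section 8).

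All of this stands, and it narrows the point. It does not remove it. None of these safeguards restores the later imaging, antibody and symptom assessments or the recording of new non-serious AEs. Section 8.8 justifies the sample size by infrequent treatment-related AEs, not by SAEs alone. A SAP can flag or reweight patients but cannot supply assessments that were not made.

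**Conclusion.** The point holds in a limited form. A stated rule requires that a treated patient be withdrawn on an undefined judgement about evaluability, and a second clause permits much the same. The patient remains in the Safety and ITT denominators while scheduled imaging, antibody, pain, ODI and neurological data and new non-serious AEs are no longer collected after the discontinuation visit. For crude AE incidence over all treated patients the effect can only be towards understatement. For by-visit percentages the direction is open.

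The size cannot be computed, because the documents do not say how often the clause would be used or in whom. The change from 0.3% to 0.2% shows how sensitive low-rate estimates are; it is not a forecast. It applies only to events that are non-serious, are not lumbar surgery, and would have appeared after the discontinuation visit. Under the assumed ranges in step 4 of the working, the average loss runs from about 1% to about 21% of events.

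**What to change.** 1. Delete criterion 4 of section 4.3.1, or limit it to patients who have not been injected.
2. State that doubt about whether a treated patient is evaluable is not a ground for withdrawal under the last bullet of criterion 6 either. Record it as a protocol deviation and address it in a sensitivity analysis that repeats the safety summaries without the flagged patients. Keep the main analysis on all treated patients.
3. State in sections 4.3 and 7.2.7 that treated patients who have not withdrawn consent are asked to complete the Table 3 safety assessments to Week 26.
4. Leave the consent, AE, poor-response, pregnancy and unacceptable-risk criteria unchanged.

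The sample size and the section 8.8 intervals do not change. The cost is a short amendment, possibly with revised consent wording (section 9.7), and some extra visits for patients who would otherwise have stopped. Those visits are already in the schedule. By section 1.3.1.5 each imaging visit carries 1.56 mSv. Screening, Weeks 6, 13 and 26 and a discontinuation visit make 5 × 1.56 = 7.8 mSv, the total already stated there.
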